**DOCUMENT CHANGE HISTORY**

Revision	Originator	Description of Change(s)	Date

## 1 OVERALL SYNOPSIS

Study Sponsor	The Sponsor for this investigation will be CooperVision International Limited (CVIL) [name]. The sponsor contact will be [name].
Title of Study	Refitting Biofinity multifocal contact lens wearer with MyDay multifocal contact lenses.
Protocol Number	EX-MKTG-155 ID23-62
Type of study	The study will be conducted following an interventional, prospective, open label, sequential study design.
Study Population	Required: 60 completed participants as per protocol (cohort) with a minimum of 66 to be enrolled. Planned: Up to 70 screened, with the aim of enrolling 66 participants.
Duration of study treatment	14 (-0/+3) days of daily disposable, daily contact lens wear per study contact lens type.
Inclusion Criteria	
In order to be enrolled, each participant shall meet the following criteria:
 
 
i. Age 40 years and older;
 
ii. Current multifocal contact lens wearer (other than MyDay® multifocal but can include Biofinity® multifocal);
 
iii. Spectacle refraction: Distance: Sphere: -6.00D to + 4.00D Astigmatism: 0.00D to -0.75D Near Addition: +0.75D to +2.50D
 
iv. Best corrected visual acuity of at least 20/25 in each eye.
 
 
The prospective participants will be given a Participant Information Sheet to read and an Informed Consent Form to sign prior to any evaluation.

Exclusion Criteria	
The following are specific criteria that exclude a candidate from enrolment in this study:
 
 
i. Acute and subacute inflammation or infection of the anterior chamber of the eye.
 
ii. Any eye disease, injury or abnormality that affects the cornea, conjunctiva or eyelids that would contraindicate contact lens wear;
 
iii. Corneal hypoesthesia (reduced corneal sensitivity), if not aphakic
 
iv. Severe insufficiency of lacrimal secretion (dry eyes).
 
v. Any systemic disease that may affect the eye or may be exaggerated by wearing contact lenses (e.g. acne and eczema).
 
vi. Allergic reactions of ocular surfaces or adnexa that may be induced or exaggerated by wearing contact lenses or use of contact lens solutions
 
vii. Any active corneal infection (bacterial, fungal, protozoal or viral).
 
viii. Newly prescribed (within the past 30 days) use of some systemic medications (such as antihistamines, decongestants, diuretics, muscle relaxants, tranquilizers, stimulants, anti-depressants, anti-psychotics, oral contraceptives) or new prescription eyedrops which is not rewetting/lubricating eyedrops for which contact lens wear could be contraindicated as determined by the investigator;
 
ix. Monocular participants (only one eye with functional vision) or participants fit with only one contact lens;
 

	
 
x. Subjects with slit lamp findings greater than grade 1 (e.g. edema, infiltrates, corneal neovascularization, corneal staining, tarsal abnormalities, conjunctival, anterior segment inflammation) as per ISO 11980, any previous history or signs of a contact lens related corneal inflammatory event (past corneal ulcers), or any other ocular abnormality that may contraindicate contact lens wear at the enrolment visit;
 
xi. History of corneal refractive surgery
 
xii. Enrolment of the family members of the investigator, family members of the investigator's staff, or individuals living in the households of these individuals.
 
xiii. Current wearer of the test contact lens MyDay® multifocal contact lens.
 

Planned Start Date	January 2023
Overall Study Duration	Nine months. This includes the study enrolment period, active contact lens wear period of approximately three months and study close out.
Objectives	
The primary objective of the study will be to assess handling characteristics (insertion and removal).
 
The secondary objectives will be to measure logMAR visual acuity.
 
[REDACTED]
 
[REDACTED]
 
[REDACTED]

	
[REDACTED]
 
[REDACTED]
 
[REDACTED]
 
[REDACTED]
 
[REDACTED]
 
[REDACTED]

Efficacy Endpoints	
The primary efficacy endpoints will be ease of handling over the week preceding the follow-up visit, calculated as the ease of insertion and ease of removal.
 
The secondary endpoint will be mean logMAR visual acuity calculated as the mean of distance, intermediate and near logMAR visual acuities.
 
[REDACTED]
 
[REDACTED]
 
[REDACTED]
 
[REDACTED]
 
[REDACTED]
 
[REDACTED]
 
[REDACTED]
 
[REDACTED]
 
[REDACTED]

	
[REDACTED]
 
[REDACTED]
 
[REDACTED]
 
[REDACTED]
 
[REDACTED]
 
[REDACTED]
 
[REDACTED]
 
[REDACTED]
 
[REDACTED]

	
[REDACTED]
 
[REDACTED]
 
[REDACTED]

	
[REDACTED]
		
	
[REDACTED]
		
Population Profiling Procedures	
The procedures to profile the population key characteristics will be:
 
 
Demographics and medical & ocular history (including concomitant treatment) questionnaires;
 
[REDACTED]
 
[REDACTED]
 
		
	 Single masked (participant)  Single masked (investigator)  Double masked*  Sponsor masked  Open label	 Single group  Parallel group  Crossover  Contralateral	
Reference Product	
The reference contact lenses will be Biofinity® multifocal CE marked and currently marketed in the UK planned replacement contact lenses that can worn up to 30 days of daily wear. The reference contact lenses will be used as per their CE marking.
		
Test Products	
The test contact lenses will be MyDay® multifocal CE marked daily disposable contact lenses currently marketed in the UK. The test contact lenses will be used as per their CE marking.
		
Study Visits	
The participants will attend a total of three visits over on average a four-week period (maximum five weeks).
 
The visit schedule will be as follow:
 
Visit 1 Screening/ enrolment / fitting & dispensing of Biofinity® multifocal contact lens visit.
 
Visit 2 Biofinity® multifocal contact lens follow-up & MyDay® multifocal contact lens fitting and dispensing visit (14 ± 3 days after Visit 1).
 
Visit 3 MyDay® multifocal contact lens follow-up & discharge visit (14 ± 3 days after Visit 2).
		
Keywords	
Biofinity ® multifocal, MyDay® multifocal, Refitting.
		
Regulatory Status	
The study requires Ethics Committee (EC) approval prior to initiation.
		
Responsibilities	Sponsor	
Name: CooperVision International Limited (CVIL)
 
[REDACTED]
	
	CRO and Data Management	
OCULAR TECHNOLOGY GROUP - International
 
[REDACTED]
	

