### Visit 2 – Biofinity® Multifocal Contact Lens Follow-up & MyDay® Multifocal Contact Lens Fitting and Dispensing visit (14 ± 3 days after visit 1)

The participant will return for the second study visit after having worn the first study contact lenses for 14 ± 3 days. The participant will attend the visit wearing Biofinity® multifocal contact lenses, having worn the contact lenses for a minimum of three hours prior to the appointment.

The participant's medical, ocular, contact lens wearing history and concomitant treatments will once again be reviewed. [REDACTED]

At the completion of the ocular integrity check the MyDay® Multifocal contact lenses will be inserted and worn for 10 minutes at which time the contact lens fit and vision will be assessed; [REDACTED]. If this is not achieved the participant will be discharged from the study; however, if a suitable fit is achieved the participant will then be instructed in the use of the contact lenses which will be dispensed to wear until Visit 3 as the main vision correction, aiming for at least 8 hours of wear a day for at least 5 days a week.

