### Visit 3 –MyDay® Multifocal Contact Lens Follow-up & Discharge Visit (14 ± 3 days after Visit 2).

The participant will return for the third study visit after having worn the second study contact lenses for 14 ± 3 days. The participant will attend the visit wearing MyDay® multifocal contact lenses contact lenses, having worn the contact lenses for a minimum of three hours prior to the appointment.

The participant's medical, ocular, contact lens wearing history and concomitant treatments will once again be reviewed. [REDACTED]

[REDACTED] Then the MyDay® Multifocal contact lenses contact lenses will be removed.

[REDACTED] the participant will be discharged from the study.

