### 6.4 Participant Instruction

The participant will be instructed to wear the study contact lenses daily for  $14 \pm 3$  days, remove the contact lenses at night (prior to sleep), discard them and use a new identical pair of contact lenses the following day.

The participant will be advised on normal or adaptive symptoms related to contact lens wear. [REDACTED]

[REDACTED] These are not reported as adverse events unless in the investigator's opinion they are unexpected in nature, severity or have a high rate of occurrence.

The participant will be instructed to follow standard recommendations provided to contact lens wearers:

- i. Avoid rubbing the eyes, always wash hands prior to touching the eyes or handling the contact lenses, avoid being in a dusty environment and to use sunglasses when outdoors.
- ii. Exercise care while washing the face with tap water; avoid splashing tap water into the eyes.
- iii. Do not swim with contact lenses whenever possible.
- iv. Immediately contact the investigator and schedule to return to clinic for a check-up within 24 hours if the eyes become red, irritated or painful.

The participant will be provided with instruction sheets [REDACTED]

A participant using re-wetting eyedrops in combination with his/her habitual contact lenses will be able to continue to do so during the study.

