#### 6.6.2 VISIT 2 – BIOFINITY® MULTIFOCAL CONTACT LENS FOLLOW-UP & MYDAY® MULTIFOCAL CONTACT LENS FITTING AND DISPENSING VISIT (14 ± 3 DAYS AFTER VISIT 1)

The routine below will be followed:

- [REDACTED]  
▪ [REDACTED]  
▪ [REDACTED]  
▪ [REDACTED]  
▪ LogMAR visual acuity measurement at distance, intermediate and near (monocular and binocular)  
▪ BIOFINITY® MULTIFOCAL CONTACT LENS REMOVAL  
▪ [REDACTED] [REDACTED]  
▪ Standard distance visual acuity [REDACTED]  
▪ MYDAY® MULTIFOCAL INITIAL CONTACT LENS INSERTION AND WEAR FOR 10 MINUTES  
▪ [REDACTED]  
▪ [REDACTED]  
▪ Standard distance, intermediate and near visual acuity with contact lenses (monocular & binocular)  
▪ Study contact lens prescription suitability evaluation & decision to dispense or change contact lens power  
▪ MYDAY® MULTIFOCAL REMOVE INITIAL CONTACT LENS & INSERT MYDAY® MULTIFOCAL SECOND CONTACT LENS AND WEAR FOR 10 MINUTES  
▪ [REDACTED]  
▪ [REDACTED]  
▪ Standard distance and near visual acuity with contact lenses (monocular & binocular)  
▪ Study contact lens prescription suitability evaluation & decision to dispense or change contact lens power  
▪ Instruction for use  
▪ Study product dispensing  
▪ Scheduling

 [REDACTED]

[REDACTED]

[REDACTED]

[REDACTED]

[REDACTED]

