### 6.6.3 VISIT 3– MYDAY® MULTIFOCAL CONTACT LENS FOLLOW-UP & DISCHARGE VISIT (14 ± 3 DAYS AFTER VISIT 2)

The routine below will be followed:

- [REDACTED]
- [REDACTED]
- [REDACTED]
- [REDACTED]
- [REDACTED]
- LogMAR visual acuity measurement at distance, intermediate and near (monocular and binocular)
- MYDAY® MULTIFOCAL® CONTACT LENS REMOVAL
- Safety ocular integrity
- Standard distance visual acuity [REDACTED]
- Discharge

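### Does the mismatch between 14 (-0/+3) and 14 ± 3 days of wear per lens affect the analysis?

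*Combined protocol and SAP*

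**What the plan says.** Section 1, row on duration of study treatment: "14 (-0/+3) days of daily disposable, daily contact lens wear per study contact lens type".

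Six other places give 14 ± 3 days:

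- Section 1, Study Visits: "fitting and dispensing visit (14 ± 3 days after Visit 1"), with the same tolerance for Visit 3 counted from Visit 2.
- Section 6.2, Visit 2: "The participant will return for the second study visit after having worn the first study contact lenses for 14 ± 3 days".
- Section 6.2, Visit 3: "The participant will return for the third study visit after having worn the second study contact lenses for 14 ± 3 days".
- Section 6.4: "The participant will be instructed to wear the study contact lenses daily for", followed by 14 ± 3 days.
- Section 6.6.2, heading: "FITTING AND DISPENSING VISIT (14 ± 3 DAYS AFTER VISIT 1").
- Section 6.6.3, heading: "DISCHARGE VISIT (14 ± 3 DAYS AFTER VISIT 2").

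The Study Visits row also puts the three visits "over on average a four-week period (maximum five weeks").

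On deviations, Section 13.2.2 (iii) makes a timing departure reportable if it could affect safety, efficacy or the experimental design. Section 13.2.3 (ii) makes it minor if it would not. Neither names a visit window. Sections 12.2 and 12.4 have the monitor check compliance during the study and see that departures are documented.

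**The concern.** The two forms cannot be explained as wear time in one place and appointment tolerance in the other. Section 6.2 (Visits 2 and 3) and Section 6.4 attach ± 3 to days of wear, which is the quantity in the synopsis row. A follow-up on day 12 therefore meets one statement and breaches the other, and the document has no rule on which prevails.

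At stake would be whether a deviation is recorded for such a participant. By extension, the question is whether that participant counts among the 60 who complete in line with the protocol (Sections 1, 5.2 and 7.1). The study is open label and the detailed analysis plan is due only before database closure. One could therefore fear that the reading is chosen after ratings have been seen.

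**Working it through.** **Inputs.** Wear per lens: 14 (-0/+3) in the synopsis duration row, and 14 ± 3 in the synopsis visit schedule and Sections 6.2, 6.4, 6.6.2 and 6.6.3. Overall time: four weeks on average, five at most (Section 1). Recall period: the week before follow-up (Section 2.4). Sample size inputs (Section 7.1): standard deviation of the difference 9.6 for insertion and 14.7 for removal, margin -7, one-sided alpha 2.5%, power 90%, no true difference.

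**1. Where the windows differ.**

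| | Days per lens | Two lenses in total |
|---|---|---|
| 14 (-0/+3) | 14 to 17 | 2 × 14 = 28 to 2 × 17 = 34 |
| 14 ± 3 | 14 − 3 = 11 to 17 | 2 × 11 = 22 to 2 × 17 = 34 |

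The sets differ on days 11, 12 and 13 only. Days 14 to 17 satisfy both, and days before 11 or after 17 satisfy neither.

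**2. The overall timeline.** Five weeks is 35 days, and both totals end at 34. A four-week average, 28 days, is the midpoint of 22 to 34. It is also reachable under 28 to 34 if nearly all visits fall on day 14. The timeline contradicts neither window and does not choose between them.

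**3. The sample size.** The plan's figure is 49. For a one-sided paired t-test, power at n is the probability that a noncentral t variable with n − 1 degrees of freedom and noncentrality 7√n / SD exceeds the 97.5% point of central t.

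- Removal, SD 14.7: the normal approximation gives (14.7 × (1.960 + 1.282) / 7)² = 46.3, so 47. With the t distribution, n = 48 gives 89.8% and n = 49 gives 90.4%. The stated 49 is reproduced.
- Insertion, SD 9.6: the t-based requirement is 22, so removal governs.

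No term in the formula depends on the visit window.

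**4. The endpoint.** A rating at day d covers days d − 6 to d. At day 11 that is days 5 to 11, wholly within wear of the current lens, with 11 − 7 = 4 earlier days of wear. At day 14 there are 7 earlier days, and at day 17 there are 10. The recall week never reaches back into the previous lens.

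**5. Deviation status of a day-12 visit.** Under 14 ± 3 there is no deviation. Under 14 (-0/+3) there is one, graded by its effect under Sections 13.2.2 and 13.2.3. Since the endpoint is still measured over a full week in the assigned lens (step 4), item (ii) of Section 13.2.3 is the natural home. The realistic difference is one minor entry in the deviation log.

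**6. Membership of the 60.** Section 5.2 uses 60 as a completion target. Section 7.2 does not restrict the comparison to a per-protocol set, and no section removes a participant for visit timing. Even if some were removed, 60 − 49 = 11 participants separate the target from the calculated requirement.

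**The case for a change.** The strongest case for a change starts from the fact that treatment duration is a basic design element and the conflict is explicit. The minus zero in the synopsis looks deliberate, and six mentions against one is not a rule of precedence. A monitor who must document non-compliance cannot tell from the text whether day 12 is compliant. Section 7.1 asks for 49 who complete in line with the protocol, so who counts could depend on the reading, even though the number does not. In an open-label non-inferiority comparison, inclusion is best fixed early, and the remedy is cheap.

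The contradiction stands, and so does the uncertainty over logging. The rest is weaker. The effect on the cohort needs an exclusion rule for visit timing that the text does not contain. Deciding which departures matter belongs in the detailed analysis plan announced in Section 7.2, and it would be needed with a single consistent window too. The fear of a late choice also sits badly with Sections 12.2 and 12.4, which have compliance reviewed and departures documented while the study runs. Nor do the sections that staff work from at the visits (6.2, 6.4, 6.6.2, 6.6.3) disagree among themselves.

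**Conclusion.** The inconsistency is real but clerical. It is confined to one synopsis cell and to three days, 11 to 13, at each of two follow-up visits. Its likely consequence is a difference in whether a minor deviation is logged. Required sample size, power, alpha, margin and the one-week recall endpoint are the same under either statement, so no change to the design or the analysis follows. The passages must be reconciled in the ordinary course of document upkeep. This review does not say which window is right.

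The conclusion rests on three assumptions. First, the detailed analysis plan, which is not part of this document, settles which timing departures, if any, affect the analysis set. Second, departures are documented as they occur, as Sections 12.2 and 12.4 intend. Third, handling ratings do not depend materially on whether 4 or 7 days of wear precede the recall week. The document gives no data on this. If they did, the actual visit days would drive the effect, not the wording of the synopsis. The number of participants affected cannot be estimated, since no distribution of visit days is given.

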## 2 INTRODUCTION AND RATIONALE

### 2.1 *Background*

Biofinity® multifocal contact lenses and MyDay® multifocal contact lenses are two successful contact lenses to correct presbyopia currently CE marked and on the UK market. Biofinity® multifocal contact lenses fitting is based upon the selection of the optimal contact lens from the choice of eight different near additions. MyDay® multifocal a more recently developed contact lens only uses three near addition designs to fit the same population of presbyopes. The simpler fitting system results in less chair time for both the eyecare practitioner and the patient. A very large number of presbyopes are currently successfully wearing Biofinity® multifocal contact lenses, the question is therefore to understand if wearers who have successfully adapted to wearing Biofinity® multifocal contact lenses could also be successful wearers of MyDay® multifocal.

### 2.2 *Objective*

The primary objective of the study will be to assess handling characteristics (insertion and removal). The secondary objectives will be to measure logMAR visual acuity.

### 2.3 *Hypotheses*

The primary hypothesis is that the ease of handling (EOH) at both insertion and removal of the test contact lens is non-inferior to the reference contact lens.

The secondary hypothesis is that high luminance, high contrast logMAR visual acuity at Distance, Intermediate and Near (logMARDIN) of the test contact lens is non-inferior to control contact lens.

### 2.4 *Endpoints*

The primary efficacy endpoints will be ease of handling over the week preceding the follow-up visit, calculated as the ease of insertion and ease of removal.

The secondary endpoint will be mean logMAR visual acuity calculated as the mean of distance, intermediate and near logMAR visual acuities.

#### 3.6 Independent Ethics Committee

Before clinical study initiation, this protocol, information given to participants (PIS), the informed consent (ICF) forms and any advertisements planned for participant recruitment will be submitted to an Independent Ethics Committee (IEC) for approval. The IEC will be provided with all information as required by local regulations and/or the IEC. At the end of the study, the Investigator will notify the IEC about the study's completion. The IEC also will be notified if the study is terminated prematurely. Finally, the Investigator will report to the IEC on the progress of the study at intervals stipulated by the IEC.

The study will be submitted to the Integrated Research Application System (IRAS) centralised National Research Ethics Service for review. The investigation will not start until the no objection notification has been received.

The Investigator will provide documentation of the IEC approval to the sponsor. The approval will be dated and will identify the applicable protocol, amendments (if any), informed consent form, all applicable recruiting materials, written information for participants, and participant compensation programs.

## 4 STUDY MATERIAL

### 4.1 Reference Contact Lenses

The reference contact lenses will be Biofinity® multifocal CE marked and currently marketed in the UK planned replacement contact lenses that can worn up to 30 days of daily wear. The reference contact lenses will be used as per their CE marking. Details of the material properties and contact lens design are given in Table 1A.

**Table 1A – Reference Contact Lenses**

	Biofinity® multifocal
Manufacturer	CooperVision Inc.
USAN material name	Comfilcon A
Water content	48%
Oxygen Permeability	142 Dk/t (at -3.00D)
Diameter (mm)	14.0mm
Base curve (mm)	8.6mm
Power (D)	6.00D to -8.00D (0.50D steps after -6.00D)
Add power	+1.00, +1.50, +2.00, +2.50
Lens Design	Multifocal / Balanced Progressive™ Technology
Indications	Daily wear soft contact lens

The contact lenses will be worn on a daily disposable modality, that is the contact lenses will be worn during the day, removed and discarded at the end of each day before sleep, a similar new pair of contact lenses being used each day as per the user instructions [REDACTED]

### 4.2 Test Contact Lenses

The test contact lenses will be MyDay® multifocal CE marked and currently marketed in the UK daily disposable contact lenses. The test contact lenses will be used as per their CE marking. Details of the material properties and contact lens design are given in Table 1B.

**Table 1B – Test Contact Lenses**

	MyDay® multifocal
Manufacturer	CooperVision Inc.
USAN material name	stenfilcon A
Water content	54%
Oxygen Permeability	$80 \times 10^{-11}$ (cm  /sec) x (ml O 2 )/(ml x mm Hg)
Diameter (mm)	14.2mm
Base curve (mm)	8.4mm
Power (D)	
Distance	+4.00 to -6.00D in 0.25 steps
Near Add	Low, medium and high

Lens Design	Multifocal / Binocular Progressive System™
Indications	Daily wear soft contact lens

The contact lenses will be worn on a daily disposable modality, that is the contact lenses will be worn during the day, removed and discarded at the end of each day before sleep, a similar new pair of contact lenses being used each day as per the user instructions [REDACTED]

## 5 STUDY POPULATION

### 5.1 Recruitment Procedure

The prospective participants will be selected from the existing clinical population of the OCULAR TECHNOLOGY GROUP- *International* clinic. The participants fulfilling the criteria for inclusion and none of the exclusion criteria will be invited in a random fashion to participate in the study until the study population is achieved. In addition, the study will be advertised in social media and / or the local press to help with recruitment.

The prospective participants from OCULAR TECHNOLOGY GROUP- *International* will initially be contacted by e-mail and if they indicate they are interested in taking part, the investigation will be explained in detail by telephone; if they then confirm their interest, a screening / enrolment / dispensing visit will be scheduled. A copy of the Participant Information Sheet [REDACTED] and Informed Consent [REDACTED] will be sent to the prospective participants for information at least 24 hours prior to the visit.

The prospective participants responding to the approved advertisement by contacting the clinic via e-mail or telephone and indicating that they are interested in taking part, will be explained the study in detail by telephone; if they then confirm their interest a screening / enrolment / dispensing visit will be scheduled. A copy of the Participant Information Sheet and Informed Consent will be sent to the prospective participants for information at least 24 hours prior to the enrolment visit.

The prospective participants will be given a Participant Information Sheet to read and an Informed Consent to sign prior to any evaluation.

